The index date was defined as the date of first occurrence of GCA code and cases were considered being incident if the GCA code first occurred after a minimal follow-up of 2 years. A treatment sequence was defined as the start of a new drug or the resumption of the same drug after a stop of drug dispensing ≥ 3 months. Annual incidence rates were calculated for the period 2009 to 2015 by using the people recorded in the EGB database as denominator.

Briefly, the results were the following: among the 752,717 patients recorded in the EGB database, 241 people fulfilled inclusion criteria with a mean follow-up of 3.7 (± 2.6) years. Annual incidence was ranging between 7 and 10/100,000 people ≥ 50 years-old that is 2300 patients/year. Demographic analyses showed that 72% of the patients were females and that mean age was 77.5 (± 8.9) years. 74.3% of the patients had at least one proxy (i.e ICD-10 code or a treatment) for hypertension, 39.4% for depression/insomnia and 33.6% for osteoporosis. After index date, temporal artery biopsy (TAB) was performed in 43.2%, high-resolution color Doppler ultrasound in 35.3% and 18FDG-positron emission tomography (PET) in 11.6%.

Regarding treatments, 84.3% of the patients used only GCs while 16.7% also received 1 to 3 adjunctive medications, mainly MTX. Mean 1st GCs sequence duration was 17.2 months (± 16.5) in 96.6% of the patients.

EGB database strengths included comprehensive patient demography, epidemiology, diagnostic methods and treatment sequences. In contrast, limited data were available for comorbidities (as only proxies were described), clinical presentations (cranial, polymyalgia rheumatica [PMR], extracranial), clinical forms (relapsing, GCs-dependant), doses of GCs used, cumulative GCs doses and GCs associated toxicities. In addition, patient journey was poorly described given that patients may be first seen by a variety of physicians according to their first signs and symptoms (e.g. ophthalmologist for blurred vision, neurologist for headache, etc.), data which was not available in the EGB database analysis.

The proportions of use of TAB, Ultrasound or PET have also to be confirmed as they thought to be unusually performed in the EGB analysis.

We propose to conduct an observational study aiming to describe GCA management and patient characteristics in France.

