- Proportion of patients with at least one general sign at diagnosis and the proportion of each sign (fever $>$ 38°C with no other etiology than GCA, weight loss and its value (%), alteration of the general condition)

For the value of ESR and CRP at diagnosis, only value measured in the previous month, the current month and the month following the date of diagnosis will be considered. For values at inclusion, only measures done within 6 month before the date of inclusion will be considered.

A listing of other initial characteristics related to GCA at diagnosis will be presented.

- Clinical form:
 - Proportion of patients with at least one relapse
 - In patient with at least one relapse:
 - Number of relapses per patient
 - Time between first relapse and diagnosis (months) ([APPENDIX](#))
 - Mean time between 2 consecutive relapses (months) ([APPENDIX](#))
 - The following information will be summarized by relapse:
 - Proportion of used criteria to assess relapse (Clinical/ Biological/ Imagery/ Other)
 - Proportion of patients using GCs just before the relapse
 - GCs dose at relapse diagnosis (mg/day)
 - Proportion of relapses of patients with Immunosuppressants just before the relapse
 - Proportion of relapses of patients with Targeted biologic therapy just before the relapse
 - Proportion of relapses of patients using other treatments just before the relapse
 - Proportion of relapses for which Glucocorticoids (GCs) were used as medical care for the relapse
 - GCs dose used for relapse medical care (mg/day)
 - Proportion of relapses for which Immunosuppressants were used as medical care for the relapse
 - Proportion of relapses for which Targeted biologic were used as medical care for relapse
 - Proportion of relapses for which other GCA (HORTON) treatments were used as medical care for relapse.
 - Distribution of GCs dependence
 - Current dose at inclusion (mg/day)
 - Number of kinetics per patient since diagnosis
 - Time between first kinetic and diagnosis (months) ([APPENDIX](#))
 - Proportion of patients with at least one kinetic ongoing at inclusion
 - Mean time between 2 consecutive kinetics (months) ([APPENDIX](#))
 - Total cumulative GCs dose according to investigator (excluding IV bolus) since diagnosis (mg) ([APPENDIX](#))
 - The following information will be summarized by Kinetic:
 - Kinetic duration (months) ([APPENDIX](#))
 - Proportion of kinetics with IV initial administration (bolus) (Yes/No)
 - If yes, total number of days

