8 STATISTICAL APPENDICES

APPENDIX (Derived data)

The following derived data will be calculated and included in the listings:

(1) **Enrollment duration**

Enrollment duration (days) = date of inclusion of the last patient – date of inclusion of the first patient

(2) **Time between first medical events related to GCA and diagnosis**

For prevalent patients (not newly diagnosed):

Time between first medical events related to GCA and diagnosis (months) = date of diagnosis – date of first medical events related to GCA

For incident patient (newly diagnosed):

Time between first medical events related to GCA and diagnosis (months) = date of diagnosis (in MM/YY format) – date of first medical events related to GCA

The date of diagnosis which is in format (DD/MM/YYYY) will be transformed into (MM/YYYY)

(3) **Time between diagnosis and inclusion**

For prevalent patients:

Time between diagnosis and inclusion (months) = (date of inclusion – date of diagnosis)/30.4375

If the date of diagnosis in format (DD/MM/YYYY) is not completed, the diagnosis date in format (MM/YYYY) will be used and the inclusion date will be transformed into (MM/YYYY).

For incident patients:

Time between diagnosis and inclusion (months) = (date of inclusion – date of diagnosis)/30.4375

The date of diagnosis in format (DD/MM/YYYY) will be used.

(4) **Duration of treatment taken**

Duration of treatment taken (months) = End date – start date +1

if ongoing treatment at inclusion:

Duration of treatment taken = Date of inclusion – start date +1

For this calculation, the date of inclusion which is in format (DD/MM/YYYY) will be transformed into (MM/YYYY) as the start date of treatment.

(5) **Time between first relapse and diagnosis**

Time between first relapse and diagnosis (months) = date of first relapse after diagnosis – date of diagnosis.

For this calculation, the date of diagnosis (for incident patient) which is in format (DD/MM/YYYY) will be transformed into (MM/YYYY) as the date of relapse.

(6) Mean time between 2 consecutive relapses

Time between 2 consecutive relapses (months) = [date of relapse (i+1) – date of relapse (i)]/(Total number of relapses per patient-1)

(7) Time between first kinetic and diagnosis

Time between first kinetic and diagnosis (months) = date of initiation of first kinetic – date of diagnosis

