For this calculation, the date of diagnosis (for incident patients) which is in format (DD/MM/YYYY) will be transformed in to (MM/YYYY) as the date of kinetic.

(8) Mean time between 2 consecutive kinetics

Mean time between 2 consecutive kinetics (months) = [date of kinetic (i+1) – date of kinetic (i)]/Total number of kinetics per patient

(9) Duration of kinetic

Duration of kinetic (months) = Stop date of kinetic – Initiation date of kinetic +1

if ongoing kinetic at inclusion:

Duration of kinetic (months) = Date of inclusion – Initiation date of kinetic +1

For this calculation, the date of inclusion which is in format (DD/MM/YYYY) will be transformed in to (MM/YYYY) as the Initiation date of kinetic.

(10) Total cumulative GCs dose since diagnosis

Total cumulative GCs dose (mg) = Σ Cumulative dose according to the investigator (excluding IV bolus) taken in each kinetic since diagnosis

(11) Age

Age (years) = (date of inclusion – birth date)/365.25 and truncated to the lowest whole integer.

(12) BMI

BMI (kg/m²) = Current weight (kg)/ [Height (cm)/100]² and rounded to the nearest decimal.

(13) Number of years since the medical school graduation

Number of years since graduation (years) = Year of inclusion date – year of medical school graduation

(14) **FACIT-Fatigue score**

The FACIT-Fatigue is an instrument that measures overall fatigue and its effects on the general functioning and daily activities through 13 questions.

The FACIT-Fatigue is a patient-reported rating scale of 13 items rated from 0 (not at all) to 4 (very much), including 11 negative items with a reversed score for calculating the score:

N° item	Reversed item?	Not at all	A little bit	Some what	Quite a bit	Very much
1	Yes	4	3	2	1	0
2	Yes	4	3	2	1	0
3	Yes	4	3	2	1	0
4	Yes	4	3	2	1	0
5	Yes	4	3	2	1	0
6	Yes	4	3	2	1	0
7	No	0	1	2	3	4
8	No	0	1	2	3	4
9	Yes	4	3	2	1	0
10	Yes	4	3	2	1	0
11	Yes	4	3	2	1	0
12	Yes	4	3	2	1	0
13	Yes	4	3	2	1	0

The total score of FACIT-Fatigue varies from 0 to 52 and is calculated with respect to the items answered:

$$[(\Sigma \text{Answered items scores}) / \text{number of items answered}] * 13$$

This calculation method allows for the management of missing data and remains acceptable if more than 50% of the items (i.e. at least 7 items) have been answered¹.

A score of less than 30 indicates severe fatigue. The higher the score, the better the quality of life is.

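### SAP derived item (8), mean time between consecutive kinetics, appears to run from start to start, so it mixes course length with time off glucocorticoids, and it divides by one interval too many

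*SAP*

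**What the plan says.** SAP 5.5.2 lists "Mean time between 2 consecutive kinetics (months") among the items describing glucocorticoid dependence, and Table 18 carries the row. In section 8, item (8), the numerator is "date of kinetic (i+1) – date of kinetic (i"), and the full definition is ["date of kinetic (i+1) – date of kinetic (i)]/Total number of kinetics per patient". Neither place says which date of a kinetic is meant or whether the interval is a period off treatment.

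Three neighbouring items in section 8 help to read it:

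- Item (7), time from diagnosis to the first kinetic, is "date of initiation of first kinetic – date of diagnosis". Its format note says the diagnosis date "will be transformed in to (MM/YYYY) as the date of kinetic". The date of a kinetic is thus equated with its initiation date.
- Item (9) gives each kinetic two dates: "Duration of kinetic (months) = Stop date of kinetic – Initiation date of kinetic +1".
- Item (6), the matching relapse item, is ["date of relapse (i+1) – date of relapse (i)]/(Total number of relapses per patient-1").

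Table 19 reports kinetic duration and, separately, whether corticotherapy was restarted after the kinetic.

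**The concern.** A relapse is recorded with a single date, so a date-to-date difference is the natural interval in item (6). A kinetic is an episode with a beginning and an end. Carrying the same form over to item (8) gives course length plus time off, under a label that can easily be read as time off alone. Under the heading of glucocorticoid dependence, a reader is likely to take the row as showing how soon treatment had to be resumed. Patients with very different histories can share one value, and no other planned output gives the time from stopping to restarting.

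The divisor is a second fault in the same line. Because it is the number of kinetics and not the number of intervals, the result is too small even if start-to-start is what the sponsor wants, and the shortfall varies with the number of kinetics.

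**Working it through.** The documents give no numerical result for this variable, so there is no stated figure to reproduce. The check applies item (8) as written.

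**Notation.** D is course duration counted as in item (9), with the initiation and stop months both included. g is the number of whole calendar months off before the next course. K is the number of kinetics. The start-to-start interval is S = D + g. Item (8) shows no summation sign; I assume the intervals are summed over i = 1 to K-1.

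- Item (8) as written: (K-1) × S / K
- Start-to-start with the item (6) divisor: S
- Glucocorticoid-free interval with divisor K-1: g

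**1. Different histories, same value (K = 2).** Number months from the first initiation as month 1.

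| Patient | Stop month | Months off | Next initiation | S | Item (8) | Time off |
|---|---|---|---|---|---|---|
| A | 24 | 1 | 26 | 25 | 25/2 = 12.5 | 1 |
| B | 6 | 19 | 26 | 25 | 25/2 = 12.5 | 19 |

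**2. Effect of the divisor.** The reported value is (K-1)/K of the true mean interval: 1/2 at K=2 and 2/3 at K=3. Two patients with identical spacing but different K therefore get different means.

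**3. Illustration.** Protocol section 1 reports from the earlier EGB database analysis: "Mean 1st GCs sequence duration was 17.2 months" (SD 16.5). That analysis counted resumption of a drug as a new sequence after a stop of at least 3 months. I borrow D = 17.2 and g = 3 as assumptions; they are not kinetic data from this study.

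S = 17.2 + 3 = 20.2 months. Item (8) then gives:

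- K=2: 20.2 × 1/2 = 10.1
- K=3: 20.2 × 2/3 = 13.5
- K=4: 20.2 × 3/4 = 15.15
- K=5: 20.2 × 4/5 = 16.16

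If instead a single interval were divided by K, the values would be 10.1, 6.7 and 5.05 at K = 2, 3 and 4.

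**4. Range at K=2.** With g = 3, item (8) gives 4.5 months for D = 6, 7.5 for D = 12 and 13.5 for D = 24. Over D from 6 to 24 and g from 0 to 6, it runs from (6+0)/2 = 3.0 to (24+6)/2 = 15.0.

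**5. Correcting one part only (D = 17.2, g = 3).**

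- Divisor K-1 alone: 20.2 months, a correct time between initiations but not a gap.
- Stop date alone, divisor K kept: 3 × 1/2 = 1.5 at K=2 and 3 × 2/3 = 2.0 at K=3, both wrong.
- Both changes: 3.0 months.

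**The case against.** The strongest reply is that start-to-start is a legitimate measure of spacing between episodes, in line with items (6) and (7). The documents do not define a kinetic, do not say that kinetics are always separated by time off treatment, and do not describe this row as a treatment-free gap. That stands: the choice of interval cannot be called an error, only undefined and poorly labelled. The reply does not reach the divisor.

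The impact is also limited. The row is descriptive and secondary, and it is not a candidate factor in either logistic regression. Table 18 also gives current dose, number of kinetics, ongoing kinetics and cumulative dose. Table 19 gives duration and restarts.

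Three stronger readings are tempting and are not supported:

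- A reader might infer that a 3-month gap would be reported as about 20 months. That is the interval before division; the written formula gives 10.1 at two kinetics and 13.5 at three.
- A reader might infer that for back-to-back courses the row merely repeats the Table 19 duration. Even before division, the +1 in item (9) breaks this when the next course starts in the stop month: the start-to-start interval is then D - 1. It equals D only if the next course starts the month after.
- A reader might infer that the row points the wrong way for dependence. That needs the joint distribution of course length and time off, which the documents do not give.

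**Conclusion.** The point holds in a limited form. On the initiation-date reading, item (8) includes the preceding course and cannot distinguish a quick restart from a long one: patients A and B both score 12.5 months although their time off is 1 and 19 months. This rests on taking the date of a kinetic from item (7), since item (8) leaves it open. Independently of that reading, and with intervals summed, the divisor K understates the mean interval: the shortfall is 1/K, so 50% at two kinetics and 33% at three. The 10.1 and 13.5 month figures rest on borrowed EGB inputs and only illustrate the size. The point deserves correction before the analysis is run because the row would otherwise be hard to interpret, but it touches no primary endpoint, model or other derived variable.

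**What to change.** Amend section 8, item (8), and the matching lines in SAP 5.5.2 and Table 18:

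1. State which date is the date of a kinetic.
2. Report *Mean glucocorticoid-free interval between consecutive kinetics (months)* for patients with K ≥ 2: the sum over i = 1 to K-1 of [initiation of kinetic (i+1) minus stop of kinetic (i)], divided by K-1. Count months consistently with item (9): because the +1 there treats the stop month as on treatment, subtract 1 from each difference and set a floor of 0. Patients A and B then give 26 - 24 - 1 = 1 and 26 - 6 - 1 = 19.
3. If the start-to-start interval is wanted, show it as a separate row labelled *time between initiations*, also divided by K-1.

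The cost is one derivation and one or two row labels. The initiation and stop dates are already used in item (9), so nothing new is collected. An ongoing last kinetic causes no loss, because only the stop dates of the earlier kinetics enter. The downside is that an interval whose stop date is unknown, and not completed under the SAP 5.2.2 date rules, becomes missing. For such patients the divisor should be the number of intervals available, and the number missing should be shown.

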4.2 Patient population

A total of 300 patients meeting the selection criteria listed below will be included in the study.

4.2.1 *Inclusion criteria*

Patients must meet the following criteria to be included in the study:

- » At least 50 years old.
- » Suffering from GCA as per investigator judgement, newly diagnosed or not.
- » Starting or under treatment for GCA.

- » Informed verbally and in writing about this study and not objecting to their data being electronically processed or subjected to data quality control.

4.2.2 *Non-inclusion criteria*

Patients fulfilling the following criteria cannot be included in the study:

- » Unable to consent
- » Participation to a randomised controlled clinical trial

4.2.3 *Withdrawal from the study*

In this cross-sectional study, no specific criteria are defined for withdrawal from the study. The patient can refuse at any time that his/her data are analysed.

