5.3.1 Case report form

No information related to patient identity (initials, full date of birth, etc) will be entered in the eCRF.

The following information will be recorded in the eCRF using the data available in the medical file or collected during the visit (as part of the routine patient management):

- » Date of the inclusion visit (the only study visit) and type of visit (outpatient visit, day hospital, in-patient hospitalisation).
- » Patient eligibility criteria.
- » Demographic data:
 - Year of birth, gender,
 - Smoking status (smoker, never smoker),
- » Clinical data:
 - Height, weight (at diagnosis, at the inclusion visit)
 - Medical history:
 - significant past and current comorbidities (e.g. diabetes, high blood pressure, dyslipidaemia, osteoporosis, neuropsychiatric disorders,

depression, insomnia, serious infection disease, parasitic diseases, cancer, stroke, coronary artery disease, ischemic cardiopathy, peripheral artery diseases, adrenal insufficiency, cataract, glaucoma, gastro-intestinal ulcer, digestive perforation, other significant history),

- start and stop date (month, year) of comorbidities
- Comorbidities related to GCs for GCA patients (i.e. which appeared or worsened during GCs treatment according to the investigator judgement).

» GCA patient journey:

- Incident or prevalent patient:
 - Newly diagnosed (i.e. incident) patient will be defined as patient with GCA diagnosis within the last 6 weeks before visit
 - Not newly diagnosed (i.e. prevalent) patients will be defined as patient with GCA diagnosis more than 6 weeks before visit
- Date of initial diagnosis
- Date of GCA signs/symptoms (month and year)
- Physician(s) who referred the patient (General Practitioner, Ophthalmologists, Neurologist, Emergency, Internist, Rheumatologist, Other).

» GCA characteristics:

- Initial presentation at diagnosis and inclusion visit:
 - Cranial (localized headache, scalp tenderness, temporal artery tenderness or decreased pulsation, ischemia-related vision impairment / loss, mouth or jaw pain upon mastication, stroke or transient ischaemic attack (TIA), other)
 - PMR (morning stiffness and/or pain in the shoulder and/or pelvic girdles, inflammatory arthromyalgia, peripheral arthritis, other)
 - Extracranial (large-vessel GCA i.e. thoracic or abdominal aortic aneurysm, myocardial infarction, dilatation, limb claudication, subclavian stenosis, other)
 - ESR/CRP
 - General signs: fever, weight loss (%), health status modification

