3.5 Patient selection

3.5.1 Patient selection method

Physicians will start patient inclusion only when the study is initiated at their site and when all regulatory authorisations are obtained.

It is expected that 300 patients (prevalent or incident cases) will be recruited in this study. Based on the previous EGB database analysis, there are 2300 incident patients/year in France. Thus, including 300 incident and prevalent patients during the recruitment period, even excluding summer holidays, seems realistic

Each physician will be requested to include consecutively during the inclusion period all the patients meeting the eligibility criteria listed below and accepting to participate in the study.

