The percentages are calculated compared to filled data
STUDY : CHUGAI-ARTEMIS - Edition date: DDMMYY
Pgm : EFFICACYGCA.SAS

Listing 9 : Specification of other treatments used just before relapse (N= XX)

Patient ID	Number of relapse	Type of patient	Type of diagnosis	Physician who follows the patient	Specification of other treatments used just before relapse

STUDY : CHUGAI-ARTEMIS - Edition date: DDMMYY
Pgm : EFFICACYGCA.SAS

Listing 10 : Specification of other treatments used for the medical care of relapse (N= XX)

Patient ID	Number of relapse	Type of patient	Type of diagnosis	Physician who follows the patient	Specification of other treatments used as medical care for relapse

STUDY : CHUGAI-ARTEMIS - Edition date: DDMMYY
Pgm : EFFICACYGCA.SAS

Table 18 - Efficacy analysis – Clinical Form - Distribution of GCs dependance - Analysis population (N=XX)

Parameter	Statistics	Total (N=XX)
Current GCs dose at inclusion (mg/day)	Mean SD Median [Q1 ; Q3] [Min ; Max] Filled, n(%) Missing, n(%)	
Number of kinetics per patient since diagnosis	Mean SD Median [Q1 ; Q3] [Min ; Max] Filled, n(%) Missing, n(%)	
Time between first kinetic and diagnosis (months)	Mean SD Median [Q1 ; Q3] [Min ; Max] Filled, n(%) Missing, n(%)	
Patient with at least one kinetic ongoing at inclusion No Yes	n(%) n(%) Filled, n(%) Missing, n(%)	
Mean time between 2 consecutive kinetics (months)	Mean SD Median [Q1 ; Q3] [Min ; Max] Filled, n(%) Missing, n(%)	
Total cumulative GCs dose according to investigator (excluding IV bolus) since diagnosis (mg)	Mean SD Median [Q1 ; Q3] [Min ; Max] Filled, n(%) Missing, n(%)	

The percentages are calculated compared to filled data
STUDY : CHUGAI-ARTEMIS - Edition date: DDMMYY
Pgm : EFFICACY\GCA.SAS

Table 19 - Efficacy analysis – Clinical Form - Description of Corticotherapy (per kinetic) - Analysis population (N=XX)

Parameter	Statistics	Total (N=XX kinetics)
Kinetic duration (months)	Mean SD Median [Q1 ; Q3] [Min ; Max] Filled, n(%) Missing, n(%)	
Kinetic with IV initial administration (bolus) No Yes	n(%) n(%) Filled, n(%) Missing, n(%)	
If yes, Total number of days	Mean SD Median [Q1 ; Q3] [Min ; Max] Filled, n(%) Missing, n(%)	
IV bolus dose (mg)	Mean SD Median [Q1 ; Q3] [Min ; Max] Filled, n(%) Missing, n(%)	
Switch PO dose (mg/day)	Mean SD Median [Q1 ; Q3] [Min ; Max] Filled, n(%) Missing, n(%)	
Cumulative dose according to investigator (mg)	Mean SD Median [Q1 ; Q3] [Min ; Max] Filled, n(%) Missing, n(%)	

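### SAP Table 19 pools completed steroid courses with courses still running at the visit, so the reported duration understates the eventual length of the courses counted and moves with the incident/prevalent mix

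*SAP*

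**What the plan says.** The SAP appendix on derived data (section 8, item 9) gives two rules for the length of a steroid course, which it calls a kinetic. A finished course is computed as "Duration of kinetic (months) = Stop date of kinetic – Initiation date of kinetic +1". A course still running at the visit is computed as "Duration of kinetic (months) = Date of inclusion – Initiation date of kinetic +1". Dates are taken to the calendar month.

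Both results go into the table titled "Table 19 - Efficacy analysis – Clinical Form - Description of Corticotherapy (per kinetic) - Analysis population (N=XX" (SAP 9.3.2). It has one kinetic-duration row and one per-kinetic cumulative-dose row, each under a single Total column counted over all kinetics. The row is not split into completed and running courses, and no censoring method or caveat is given.

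Three other places bear on how the row will behave:

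- Protocol 4.2.1 admits only patients who meet the criterion "Starting or under treatment for GCA".
- Protocol 5.3.1 defines incident cases: "Newly diagnosed (i.e. incident) patient will be defined as patient with GCA diagnosis within the last 6 weeks before visit".
- SAP 3.5.1 fixes the total but not the mix: "It is expected that 300 patients (prevalent or incident cases) will be recruited in this study".

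For immunosuppressants, biologics and other long-term drugs, SAP 5.4 and Tables 6–11 keep treatments stopped before inclusion apart from those ongoing at inclusion.

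**The concern.** One row mixes two different quantities: the final length of finished courses and the elapsed time in unfinished ones. Its mean and median are neither the length of a completed course nor the time on treatment at the visit. Elapsed time cannot exceed final length, so the pooled figure must understate the eventual length of the courses it counts whenever any are still running. It also depends on how many newly diagnosed patients happen to be recruited, which the plan neither fixes nor forecasts. Cumulative dose per course has the same fault, because a dose to date is averaged with final doses.

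This is more than a stray secondary row. Protocol 1 calls high-dose glucocorticoids the mainstay of management, and the primary objective covers specific treatments since diagnosis. SAP 5.4 restricts the primary treatment analysis to drugs other than glucocorticoids, which leaves Table 19 as the only summary of steroid course duration. A reader could easily take it as the usual length of a course in France.

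**Working it through.** The plan states no expected duration, incident share or share of running courses for this study, so there is no figure of its own to reproduce. The check has a part that needs no model and a part that is illustrative.

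**Without a model.** An incident patient was diagnosed at most 6 weeks (42 days) before the visit. Over 42 days the calendar month changes by 0, 1 or 2 (for example, 31 January to 14 March changes by 2). With the +1, a course begun at diagnosis is recorded as 1, 2 or 3 months, whatever its final length.

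**Illustrative model: inputs**

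- Course length has mean μ = 17.2 and SD = 16.5 months. This is the first-sequence figure from the earlier claims-database study in Protocol 1, the only such figure in the documents. It is used here as an assumption, with gamma and lognormal shapes.
- Each patient is sampled once, during a running course, in steady state.
- Running courses of prevalent patients began more than 6 weeks before the visit.
- The incident share q is not given; 0–40% is tabulated.
- Completed earlier courses per prevalent patient, c, are not given; 0 and 0.5 are used.

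**Running courses**

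- CV² = (16.5/17.2)² = 0.920.
- Mean eventual length of a course caught while running: μ(1 + CV²) = 17.2 × 1.920 = 33.0 months. This exceeds 17.2 because long courses are more likely to be caught.
- Mean time so far: half of that, 16.5 months.
- About 7.8% of running courses (gamma) are within 6 weeks of their start, at a mean of about 0.69 months (42/30.4375 = 1.38, halved). The others average (16.51 − 0.078 × 0.69)/0.922 = 17.85 months.

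**Adding the SAP's +1**

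- Prevalent, running: 18.85.
- Incident: 1.69.
- Completed: 17.2 + 1 = 18.2.

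Pooled mean = [1.69q + (1 − q)(18.85 + 18.2c)] / [q + (1 − q)(1 + c)].

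For q = 0.2 and c = 0: 0.2 × 1.69 + 0.8 × 18.85 = 15.4. For q = 0.2 and c = 0.5: (0.34 + 0.8 × 27.95)/1.4 = 16.2.

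Simulation with calendar-month differences agrees with this formula to within about 0.1 month. Gamma results, in months:

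| Incident share | Pooled mean, c = 0 / 0.5 | Pooled median, c = 0 / 0.5 | Eventual mean of same courses, c = 0 / 0.5 |
|---|---|---|---|
| 0% | 18.8 / 18.6 | 14 / 14 | 34.3 / 28.6 |
| 10% | 17.1 / 17.5 | 12 / 13 | 32.7 / 27.9 |
| 20% | 15.5 / 16.2 | 10 / 11 | 31.1 / 27.1 |
| 30% | 13.7 / 14.9 | 8 / 10 | 29.4 / 26.2 |
| 40% | 12.0 / 13.4 | 5 / 8 | 27.7 / 25.3 |

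The eventual means do not include the +1. Lognormal lengths give almost the same pooled means, and medians of 12–13 falling to 5–8. In every scenario the pooled mean and median lie below the eventual values and fall as the incident share rises.

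**The case against.** The strongest counter-argument is that the plan already makes much of this visible. SAP 5.5.2 says the clinical-form endpoints, which include course duration, are also described by incident and prevalent status. Table 18 reports the share of patients with a course ongoing at inclusion. The formula is stated openly, and no test depends on the row. All of this is true, but it does not correct the overall row. The prevalent group still mixes completed and running courses, and Table 18 counts patients rather than courses. The Table 19 shell has only a Total column and, unlike Table 15, carries no note to repeat it by patient type.

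A reader might infer that the row is too short as an estimate of steroid courses in general, for instance against 17.2 months. The documents do not support that. Sampling patients on treatment over-represents long courses, which pulls the other way. In the model the pooled mean is above 17.2 with no incident patients and about equal to it at 10%. That near-equality is a coincidence of the assumed figures and does not validate the row. The plan does not propose this comparison either, and the 17.2 describes first sequences separated by dispensing gaps of at least 3 months, whereas Table 19 covers all courses.

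A reader might also extend the criticism to the other drugs, where the appendix uses "Duration of treatment taken = Date of inclusion – start date +1". Tables 7, 9 and 11 are already titled as ongoing at inclusion and kept apart from stopped treatments, so nothing is pooled there and any change would be one of wording.

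**Conclusion.** The point holds in this form: Table 19 pools elapsed time with final length, and dose to date with final dose. Two consequences follow from the rules themselves. The pooled duration understates the eventual length of the counted courses when any are running, and it shifts with the incident share when practice has not changed. The direction relative to all courses in the population is unknown.

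The size is illustrative only. It rests on the borrowed mean and SD, steady-state sampling, and assumed values for the incident share and for completed courses. Under those assumptions, going from 0% to 40% incident moves the pooled mean by about 5 to 7 months (18.6 − 13.4 = 5.2; 18.8 − 12.0 = 6.8). This affects the interpretation of a secondary descriptive result. It is worth correcting because it is the only steroid-duration summary and the correction is cheap.

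**What to change.** - In Table 19, report duration and cumulative dose in separate columns for completed and ongoing kinetics, as Tables 6–11 do for other drugs.
- Label the ongoing column *time on (dose in) current course at inclusion*.
- Add a footnote that neither column estimates the usual course length, because only patients on treatment are sampled.
- Add the instruction to repeat the table by incident and prevalent status, which SAP 5.5.2 already requires.

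Do not add a Kaplan–Meier median with running courses censored at the visit. Those courses are in the sample because they are running, so they enlarge the risk set and can never contribute an event. In the same model, where the true median is about 12.4 months, the naive estimate is about 31–36 months with 0.5 completed courses per prevalent patient and about 51–52 with 0.3. With none completed it cannot be estimated.

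The cost is small. Protocol 5.3.1 already collects glucocorticoid start and end dates, and Table 18 already uses ongoing status. Only SAP text and table shells change.
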